#### 7.8 Reporting to the Food and Drug Administration (FDA)

The Overall PI, as study sponsor, will be responsible for all communications with the FDA. The Overall PI will report to the FDA, regardless of the site of occurrence, any serious adverse event that meets the FDA's criteria for expedited reporting following the reporting requirements and timelines set by the FDA.

#### 7.9 **Reporting to Hospital Risk Management**

Participating investigators will report to their local Risk Management office any participant safety reports, sentinel events or unanticipated problems that require reporting per institutional policy.

#### 7.10 Routine Adverse Event Reporting

All Adverse Events **must** be reported in routine study data submissions to the Overall PI on the toxicity case report forms. **AEs reported through expedited processes (e.g., reported to the IRB, FDA, etc.) must** also be reported in routine study data submissions.

#### PHARMACEUTICAL INFORMATION

A list of the adverse events and potential risks associated with the investigational or other agents administered in this study can be found in Section 7.1.

#### 8.1 Mirvetuximab Soravtansine (IMGN 853)

#### 8.1.1 Description

Mirvetuximab soravtansine is an antibody-drug conjugate designed to target FR $\alpha$ . It consists of the humanized anti-FR $\alpha$  monoclonal antibody M9346A attached via a cleavable disulfide linker to the cytotoxic maytansinoid, DM4 (Figure 1).

DM4 is ~2% by weight relative to monoclonal antibody.

Due to the nature of the conjugation process, the number of DM4 molecules attached to the monoclonal antibody ranges from 1 to 7 molecules per antibody, with an average of 3 or 4 DM4 molecules per antibody. Conjugation of the maytansinoid to the tumor-targeting antibody ensures that the cytotoxic component remains inactive in the circulation. Release of the cytotoxic payload requires binding, internalization, and degradation of the antibody. The released payload then kills the cell by inducing G2-M arrest and cell death. Cellular processing of maytansinoid conjugates can also generate lipophilic catabolites that cross cell membranes and kill neighboring cells.

Figure 1: Mirvetuximab soravtansine

NCI Protocol #: N/A DF/HCC Protocol #: 18-602 Protocol Version Date: December 11, 2023

PK studies demonstrated the stability of mirvetuximab soravtansine in circulation, showed clearance via a distribution phase lasting about 24 hours followed by a slower terminal elimination phase after intravenous administration, and suggested linear PK.

#### 8.1.2 Form

The investigational study drug, mirvetuximab soravtansine, will be provided by ImmunoGen, Inc. at a protein concentration of 5.0 mg/mL in an aqueous pH 5.0 buffered solution. IMGN853 will be available in a 20 mL Type I glass vial with 20 mL deliverable volume. The container closure for the Type I glass vials will consist of a 20 mm ETFE-coated serum stopper (Flurotec®) on the top and product contact surface with a 20 mm aluminum TruEdge® seal with blue Flipoff® top. Refer to the Pharmacy Manual for labeling information.

#### 8.1.3 Storage and Stability

Mirvetuximab soravtansine should be stored upright in the carton supplied, protected from light, refrigerated at 2-8°C (36 to 46°F) until the time of preparation and should not be shaken or frozen.

Table 3 specifies the cumulative allowable time limits for specific temperature ranges and reporting requirements for IMGN853 while in storage. The total cumulative temperature excursion time for vials must be documented by the pharmacy in the applicable drug accountability logs.

Table 1: IMGN853 Storage, Temperature Excursion Allowance, and Reporting Requirements

Temperature Range	Time Duration	Allowable?	Comments
<-5.4°C	Any	No	Investigative sites to quarantine product

			and report excursion to sponsor- investigator
-5.4 to 1.4°C	Up to 24 hours	Yes	IMGN853 can be used
	(1,440 minutes)		Investigative sites to check cumulative
	cumulative		time. If less than or equal to 24 hours
			(1,440 minutes) then no reporting
			required.
1.5 to 8.4°C	Any	Yes	IMGN853 can be used.
8.5 to 25.4°C	More than 6	Yes	IMGN853 can be used.
	hours (360		Investigative sites to check cumulative
	minutes)		time. If less than or equal to 6 hours
	cumulative		(360 minutes) then no reporting
			required.
8.5 to 25.4°C	More than 6	No	Investigative sites to quarantine product
	hours (360		and report excursion and cumulative
	minutes)		time to sponsor-investigator.
	cumulative		*Use may be permitted upon review.
> 25.4°C	Any	No	Investigative sites to quarantine product
			and report excursion to sponsor-
			investigator.

**Note:** The temperature excursion allowances for onsite storage of IMGN853 do not apply during the shipment period. Any excursion outside of 2 to 8°C (36 to 46 °F) experienced during transit must be reported.

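### The mirvetuximab storage table marks one and the same temperature excursion, 8.5 to 25.4°C for more than 6 hours, as both usable and not usable

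*Combined protocol and SAP*

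**What the plan says.** Section 8.1.3 of the combined protocol and SAP (Storage and Stability, under mirvetuximab soravtansine) introduces a table that "specifies the cumulative allowable time limits for specific temperature ranges and reporting requirements for IMGN853 while in storage". It also requires the pharmacy to record total cumulative excursion time for vials in its drug accountability logs. For each temperature range the table gives a duration, a yes/no answer on whether the excursion is allowable, and a comment.

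Two adjacent rows cover 8.5 to 25.4°C, and both give the duration as more than 6 hours (360 minutes) cumulative.

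- The upper row is answered yes, with "IMGN853 can be used". Its comment tells sites to check the cumulative time and says that no report is needed "If less than or equal to 6 hours".
- The lower row is answered no, with "Investigative sites to quarantine product" and an instruction to report the excursion and its cumulative time to the sponsor-investigator. It adds "Use may be permitted upon review".

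The lead-in sentence calls this Table 3, while the caption ("Storage, Temperature Excursion Allowance, and Reporting Requirements") numbers it Table 1.

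**The concern.** The table is the instruction by which a pharmacist decides whether to release or quarantine a vial. As printed, it gives both answers for a single condition. A pharmacist who looks up an 8-hour excursion at 20°C finds a row that permits use, followed by a row that requires quarantine and a report.

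If the upper row is followed, investigational product past the 6-hour mark could reach a patient although the lower row would hold it for review. The opposite error is also possible. Because no duration entry in this range covers 6 hours or less, a strict reader has only the upper row's comment to support using a vial after a short excursion.

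The trial includes external sites, and each site orders its own supply (Sections 8.1.6 and 8.1.9; Appendix B, Section 2.2). Different pharmacies could therefore handle identical excursions differently, each with support in the text.

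**Working it through.** No statistical quantity is involved and no sample-size or error-rate formula applies. The check is a comparison of the rows in the Section 8.1.3 table.

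**1. Rows side by side (paraphrased)**

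| Range | Duration entry | Allowable | Threshold in the comment |
|---|---|---|---|
| −5.4 to 1.4°C | up to 24 h (1,440 min), cumulative | Yes | no report if 24 h or less |
| 8.5 to 25.4°C, upper row | over 6 h (360 min), cumulative | Yes | no report if 6 h or less |
| 8.5 to 25.4°C, lower row | over 6 h (360 min), cumulative | No | quarantine and report; use possible after review |

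**2. Units.** 6 h × 60 = 360 min and 24 h × 60 = 1,440 min. Both agree with the table, so the conflict does not come from a conversion error.

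**3. Conflict between rows.** The condition is identical in the two 8.5 to 25.4°C rows (same range, more than 360 cumulative minutes) and the answers are opposite. Both rows cannot apply to the same vial.

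**4. Conflict within the upper row.** Its duration entry describes times above 360 minutes. Its comment sets a reporting rule for times of 360 minutes or less. The two do not overlap, so the comment addresses a case that the row's own duration excludes.

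**5. Coverage.** In the duration column, 8.5 to 25.4°C has two entries above 6 hours and none at or below it.

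**6. Comparison with the parallel row.** In the −5.4 to 1.4°C row, the duration entry and the comment use the same limit in the same direction. The upper 8.5 to 25.4°C row has the same structure but breaks that pattern, which points to a drafting slip in its duration entry.

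**7. Reading error in the PDF.** This is unlikely. The conflict lies in words and not in an inequality sign that could be misread, and both duration entries are complete, including the minutes and the word cumulative. No other part of the document corrects the table.

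**8. Table numbers.** Table 1 is already the mirvetuximab infusion-reaction table (Section 5.3.1) and Table 3 is the ocular-disorder table (Section 6.1.1). Both numbers given for the storage table in Section 8.1.3 therefore belong to other tables.

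**The case against.** The strongest case on the other side is that the slip largely gives itself away. The upper row does not waive reporting above 6 hours: its comment removes reporting only at 6 hours or less, and the row below expressly requires quarantine and a report. To release over-limit drug, a pharmacist would have to act on the yes and overlook both the comment beside it and the next row. Two adjacent rows with the same condition and opposite answers should prompt a query, and the logging requirement leaves a record of the exposure. Moreover, the lower row allows for use after review, so passing 6 hours is not treated as automatically disqualifying. The documents contain no stability data from which harm could be shown.

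Much of this stands. A careful pharmacist may well infer the intent, the frequency of such excursions is unknown, and actual damage to the product cannot be demonstrated here. The table-number error is clerical, because the caption follows the reference closely and names the drug and topic. These points reduce the urgency but do not resolve the contradiction: the table exists to be applied by lookup, and its lookup columns give two answers.

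One further point is fair. For mirvetuximab, Section 8.1.2 cites the Pharmacy Manual only for labelling, so the documents do not show that the manual holds the excursion limits.

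**Conclusion.** The concern holds. Section 8.1.3 gives opposite dispositions for one storage condition, and the upper row also contradicts its own comment. The conflict applies to every vial with more than 6 cumulative hours at 8.5 to 25.4°C. How many vials that is cannot be estimated from the documents.

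The conclusion rests only on the printed text of the table. The practical risk rests on the further assumption that some pharmacies act on the duration and allowable columns without resolving the conflict. This is an internal inconsistency in drug handling; it touches no endpoint, error rate, sample size or analysis. It should be corrected because the table governs whether product that has been out of range may be given. This review does not say which limit is right.

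**What to change.** - Reconcile the duration entry of the upper 8.5 to 25.4°C row with its own comment and with the row below, using the product's stability information, and the Pharmacy Manual if it states these limits. After correction, the two rows should describe non-overlapping conditions.
- Give the table a unique number and correct the reference in the lead-in sentence.
- While the table is open, state what applies at −5.4 to 1.4°C beyond 24 hours, which no row covers.
- Send site pharmacies a short notice of the corrected rows.

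The main correction is one table cell, with a renumbering, a cross-reference, one clarified condition and a pharmacy notice alongside it. The design, the data collection and the analysis do not change.

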### 8.1.4 Compatibility

IMGN853 is NOT compatible with saline (0.9% sodium chloride). Therefore, dilutions must be made in 5% dextrose and 5% D-glucose. Other diluents have not been tested, and therefore, cannot be deemed compatible.

Any combination of the materials used in the fluid contact pathways (e.g., infusion bag, syringe, needle, infusion set, closed system transfer device, filter, or catheter materials) listed below are acceptable for use:

- Acetyltributylcitrate (ATBC)
- Acrylonitrile-butadiene-styrene copolymer (ABS)
- Diethylhydroxylamine (DEHA)
- Diisononyl ester (DINCH)
- Dioctyl terephthalate (DEHT or DOTP)
- Ethylene Vinyl Acetate (EVA)
- Fluorinated ethylene propylene (FEP)
- Polyacetal
- Polycarbonate
- Polyethersulfone (PES)

- Polyethylene
- Polyisoprene
- Polyolefin (e.g., polymer of ethylene and/or propylene)
- Polypropylene (PP)
- Polytetrafluoroethylene (PTFE), Acrylic
- Polytetrafluoroethylene (PTFE)
- Polyurethane (PUR)
- Polyvinyl chloride (PVC) plasticized with Di-2-ethyl-hexylphthalate (DEHP)
- Polyvinyl chloride (PVC) plasticized without Di-2-ethyl-hexylphthalate (non- DEHP)
- Silicone
- Stainless steel
- Thermoplastic elastomer (TPE)
- Trioctyl Trimellitate (TOTM or TETM)

Contact Sponsor-Investigator for materials not listed above.

#### 8.1.5 Handling

Qualified personnel, familiar with procedures that minimize undue exposure to themselves and the environment, should undertake the preparation, handling, and safe disposal of the chemotherapeutic agent in a self-contained and protective environment.

#### 8.1.6 Availability

Each site is responsible for requesting the investigational products from ImmunoGen.

#### 8.1.7 Preparation

The total dose of IMGN853 will be based upon the adjusted ideal body weight (AIBW) using the following formula:

#### Adjusted Ideal Body Weight (AIBW)

 $IBW^1 + 0.4$  (Actual weight –  $IBW^1$ )

Where:

## Ideal Body Weight (IBW)

 $IBW^{1} (male) = 0.9H^{1}-88$  $IBW^{1} (female) = 0.9H^{1}-92$ 

(H=height in cm; W=weight in kg)

The patient's weight will be collected at each cycle. Dosing will be based off the wight at baseline prior to C1D1 unless current weight is > 10% different (not influenced by weight gain

or loss attributed to fluid retention). If required per institutional policy, it is acceptable to recalculate AIBW at each cycle using the patient's current weight. Sites must clearly document the weight used to calculate dose at each cycle.

Prior to preparation, the lot expiry date should be verified via the Certificate of Analysis (CoA) or label. A visual inspection for cracks, leaks or any other damage should be done before use and any damage must be reported to the Sponsor-Investigator and ImmunoGen at [contact].

Infusion bags must be labeled with the protocol number, subject number (patient ID), storage temperature, dose, and volume of IMGN853 in the bag, or according to Institutional protocol.

# If necessary, study drug from different drug lots may be mixed in a single-dose administration.

- Remove the required number of vials from the refrigerator 25 minutes before preparation to allow IMGN853 solution for injection to reach ambient temperature (18 to 25°C)
- Keep IMGN853 vials protected from direct light
- Gently invert vials (without shaking) 8 to 10 times before withdrawing the drug
- Withdraw the required volume aseptically using an appropriate syringe and needle or CSTD (closed system transfer device)
- Choose a suitable infusion bag based on final volume for infusion.
- Dilute the drug with 5% dextrose or 5% D-glucose to a final concentration of 1 mg/mL to 2 mg/mL
  - **Important:** IMGN853 is **NOT compatible with saline** (0.9% sodium chloride). Therefore, dilutions must be made in 5% dextrose or 5% D-glucose.
- IMGN853 does not contain a preservative. Prepared study drug:
  - May be stored at room temperature but infusion must be completed within 8 hours after preparation
  - May be stored at 2 to 8°C for up to 24 hours, and once removed from the fridge it may be stored at room temperature, but the infusion must be completed within 8 hours
- If the prepared study drug is stored at 2 to 8 °C, it should be removed from the refrigerator at least 30 to 60 minutes prior to administration, to allow the solution to reach room temperature. Allow the prepared study drug to reach room temperature without warming methods.
- The total time at room temperature may not exceed 8 hours, inclusive of infusion time. Light protection is not required for prepared IMGN853. Ensure that in-line filter of 0.2 or  $0.22 \ \mu m$  is used to filter diluted IMGN853 from the bag during administration

#### 8.1.8 Administration

During combination treatment, mirvetuximab soravtansine should be administered first, followed by pembrolizumab.

- IMGN853 should be administered IV, using an IV tubing administration set with a 0.2  $\mu$ m or 0.22  $\mu$ m in-line filter.
- The infusion tubing may be primed with 5% dextrose (or 5% D-glucose) or may be primed with IMGN853, ensuring that no drug is wasted in the process.
- Following the infusion, the IV line should be flushed with 5% dextrose, or 5% D-glucose as required to ensure delivery of the full dose.

**Infusion Rate**: Initially IMGN853 should be administered at a rate of 1 mg/min; after a continuous 30 minutes of infusion, the rate can be increased to 3 mg/min if well tolerated. If well tolerated after a continuous 30 minutes of infusion at 3 mg/min the rate may be increased to 5 mg/min. Subsequent infusions may be delivered at the highest tolerated rate.

**Duration of infusion**: The overall length of infusion will vary depending on dose and patient tolerability. Patients will remain in the clinic under observation for 2 hours after the first infusion, and for at least 1 hour after each subsequent infusion of MIRV, during which pembrolizumab infusion can be administered. While in the treatment area, patients are closely monitored for AEs.

Details of the dose level and total dose administered should be documented in the source records as noted below:

- Start and stop times for each administration (end of infusion should be the time of completion of the post-dose 5% dextrose or 5% D-glucose flush)
- Infusion rate(s)
- Total calculated dose (in mg)
- Total calculated volume (in mL)
- Total volume administered (in mL)
- Times for any interruptions
- Reason if any administration is stopped prematurely or interrupted and volume administered prior to interruption.

## 8.1.9 Ordering

Investigative sites will order their own supply of mirvetuximab soravtansine.

### 8.1.10 Accountability

The investigator, or a responsible party designated by the investigator, should maintain a careful record of the inventory and disposition of the agent using the NCI Drug Accountability Record Form (DARF) or another comparable drug accountability form. (See the NCI Investigator's Handbook for Procedures for Drug Accountability and Storage.)

8.1.11 Destruction and Return

Expired investigational product will be destroyed at the site per institutional policy. Upon completion or termination of the study, all unused and/or partially used investigational product will be destroyed at the site per institutional policy.

#### 8.2 **Pembrolizumab**

#### 8.2.1 Description

Pembrolizumab is a highly selective humanized mAb designed to block the interaction between PD-1 and its ligands, PD-L1 and PD-L2. Pembrolizumab is an IgG4/kappa isotype with a stabilizing sequence alteration in the Fc region. The theoretical molecular weights of the heavy and light chains derived from the amino acid sequences, excluding glycosylation, are 49.4 kiloDaltons (KDa) and 23.7 KDa, respectively. The antibody is heterogeneously glycosylated at asparagine 297 within theFc domain of each heavy chain, yielding a molecular weight of approximately 149 KDa for intact pembrolizumab.

#### 8.2.2 Form

Pembrolizumab Solution for Infusion is a sterile, non-pyrogenic clear to slightly opalescent, colorless to slightly yellow aqueous solution supplied in single-use Type I glass vial containing 100 mg/ 4 mL of pembrolizumab. The drug product is manufactured using facilities and practices under Good Manufacturing Practice (GMP) requirements.

Pembrolizumab Solution for Infusion 100 mg/ 4 mL vial is a liquid DP (manufactured using the fully formulated DS with L-histidine as a buffering agent, polysorbate 80 as a surfactant, and sucrose as a stabilizer/tonicity modifier, and Water for Injection as Solvent). Pembrolizumab Solution for Infusion vials are filled to a target of 4.25mL (106.25mg) to ensure recovery of 4.0mL (100mg). At the point of use, Pembrolizumab Solution for Infusion is diluted with 0.9% Sodium Chloride Injection, USP (normal saline) or regional equivalent or 5% Dextrose Injection, USP (5% dextrose) or regional equivalent to 1-10 mg/mL before intravenous (IV) administration through an infusion filter.

#### 8.2.3 Storage and Stability

Pembrolizumab Solution for Infusion 100 mg/ 4 mL vial should be stored under refrigerated conditions 2°C to 8°C (36-46 °F). Vials should be stored in the original box to ensure the drug product is protected from light. Do not shake and do not freeze.

Store the diluted solution from KEYTRUDA 100 mg/vial either

- At room temperature for no more than 6 hours from the time of dilution. This includes room temperature storage of the diluted solution, and the duration of infusion.
- Under refrigeration at 2°C to 8°C (36-46 °F) for no more than 96 hours from the time of dilution. If refrigerated, allow the diluted solution to come to room temperature prior to administration. Do not shake.

Discard after 6 hours at room temperature or after 96 hours under refrigeration.

Do not freeze.

Clinical supplies must be stored in a secure, limited-access location under the storage conditions specified on the label. Receipt and dispensing of trial medication must be recorded by an authorized person at the trial site. Clinical supplies may not be used for any other purpose other than that stated in the protocol.

#### 8.2.4 Compatibility

Pembrolizumab should be prepared in 0.9% Sodium Chloride Injection, USP (normal saline) or regional equivalent or 5% Dextrose Injection, USP (5% dextrose) or regional equivalent. The final concentration of pembrolizumab in the infusion solutions should be between 1 mg/mL and 10 mg/mL. Pembrolizumab SHOULD **NOT** BE MIXED WITH OTHER DILUENTS.

See section 8.2.7 for infusion bag material compatibility.

#### 8.2.5 Handling

Qualified personnel, familiar with procedures that minimize undue exposure to themselves and the environment, should undertake the preparation, handling, and safe disposal of the chemotherapeutic agent in a self-contained and protective environment.

#### 8.2.6 Availability

Each site is responsible for requesting the investigational products from Merck.

#### 8.2.7 Preparation

Aseptic technique must be strictly observed throughout the preparation procedure. Use of a biosafety cabinet is preferred since no anti-microbial preservative is present in the product; however, it is not mandatory unless specified by site standard operating procedure.

The preferred method of dose preparation is the volumetric method. The Sponsor recommends reconstitution and administration of pembrolizumab that follows the parameters in the Pharmacy Manual, however if use of gravimetric preparation is mandatory due to local site procedures, the following requirements must be satisfied and documented:

- Draw the required volume up to 4.0 mL (100 mg) of pembrolizumab from each vial
- Limit the number of punctures of each vial to one
- For gravimetric preparation method using density of pembrolizumab solution, a value of 1.03 g/mL should be used

Use of spikes or other CSTDs (closed system transfer devices) are permitted as long as the pharmacist is aware of the hold-up volume (volume of fluid that is left in the device) and that the contact time is  $\leq$  30 min. HQ approval is only needed for spikes/ CSTDs with contact time

greater than 30 min to ensure compatibility of the device. Please note that as long as the CSTD or spike does not come into contact with the drug product during infusion, then 30 mins does not count in infusion time.

Sites may choose to select an infusion bag size based on their institutional practice provided the following conditions are met:

- Concentration of pembrolizumab is between 1 mg/mL and 10 mg/mL
- The infusion volume to bag capacity ratio should not be less than 0.3. In other words, the bag must be filled to at least 30% capacity.

A suitable infusion bag material must be chosen. The bag may be empty, or it may contain normal saline. The following infusion bag materials are compatible with pembrolizumab:

- PVC plasticized with DEHP
- PVC, DEHP free
  - Since it is still a PVC set, DEHP must be replaced with another plasticizer. If the alternate plasticizer is DEHT or TOTM then it is ok.
- Non-PVC (polyolefin)
- Ethylene-vinyl acetate (EVA)
- Polyethylene (PE) lined polyolefin
- Polypropylene (PP)
- Low density poly ethylene (LDPE)
- Clear Polyurethane (PVC Free, DEHP Free)
- Acrylic
- Polymethylmethacrylate,
- Silicone rubber with Fluorosilicone
- Polyethylene terephthalate (PET)
- Stainless steel
- Polybutadiene
- Polycarbonate (PC)
- Isoprene rubber
- Polyvinyl chloride
- Polyethersulfone (membrane pore size 0.2µm) non-PVC multilayer co-extrusion infusion bag: three layers co-extrusion infusion bag; polypropylene/ polypropylene/ polypropylene
- Acrylonitrile butadiene styrene (ABS)
- Polytetrafluoroethylene
- Dioctyl terephthalate (DOTP)

\*Contact Sponsor-Investigator for materials not listed above

To prepare the pembrolizumab infusion bag:

- 1. Calculate the volume of pembrolizumab and normal saline required to prepare the infusion (admixture) bag. The dose of pembrolizumab used in this trial is 200mg.
  - Volume of pembrolizumab (mL) = required dose amount (mg) / 25 (mg/mL)
  - Volume of normal saline = total infusion volume volume of pembrolizumab from

above

- If a bag pre-filled with normal saline is being used, remove the excess volume of normal saline using a sterile syringe (Polypropylene, latex-free) attached to a suitable needle. Keep in consideration the excess bag fill volume as well as the volume of pembrolizumab to be added to the bag to prepare the infusion solution. This helps ensure that the concentration in the bag can be accurately calculated and falls within the acceptable range of 1 mg/mL to 10 mg/ml. If the site would like to proceed without removing excess saline they must ensure that the concentration of pembrolizumab would still fall within acceptable range.
- If an empty bag is being used, withdraw the necessary volume of normal saline from another appropriate bag and inject into the empty bag. Keep in consideration the volume of pembrolizumab to be added to the bag to prepare the infusion solution.
- 2. Withdraw the required volume of pembrolizumab from the vial(s) (up to 4 mL from each vial) using a sterile syringe attached to a suitable needle. The vial(s) may need to be inverted to remove solution.
- Volume of pembrolizumab (mL) = required dose amount (mg) / 25 (mg/mL)
- Note: If it is necessary to use several vials, it is advisable to withdraw from several vials into a suitable size single use syringe using a new needle for each vial.
- Discard any unused portion left in the vial as the product contains no preservative.
- 3. Add the required pembrolizumab into the infusion IV bag containing normal saline and gently invert the bag 10-15 times to mix the solution.
- From a microbiological point of view, diluted solution should be used as soon as possible after preparation
- Pembrolizumab solutions may be stored at room temperature for a cumulative time of up to 6 hours. This includes room temperature storage of admixture solutions in the IV bags and the duration of infusion.
- IV bags may be stored under refrigeration at 2 °C to 8 °C (36 °F to 46 °F), total cumulative storage time at room temperature and refrigeration should not exceed 24 hours. (96 hours is acceptable dependent upon country approved commercial Keytruda label).

If the infusion bag is excessively handled or shaken, particulates may form. If this occurs, discard the bag and create a new bag taking care not to shake. Please contact your HQ clinical study team if particulates are noticed for further instructions. Be prepared to provide the following information:

- IV bag manufacture, lot and expiry
- Target volume of admixture solution in the IV bag (e.g. 100 mL, 200 mL etc.)
- Amount of drug product (mL or mg) added to the bag
- Drug product lot
- Brief description of the nature of visible particles (color, shape, size, numbers etc.).

To prevent the formation of particulates:

- Minimize agitation
- Ensure dilution of admixture solution is 1mg/mL to 10 mg/mL
- Minimization of headspace (empty space over the liquid) in syringes and admixture bags

• Avoid siliconized products during preparation (Please note there is particulate formation when there is over agitation of the product and when concentrations are less than 1 mg/mL)

If particles are seen in the vials, these will need to be reported as clinical supply complaints per GCD 104. If particles are seen in the admixture solution, these need to be reported to the HQ clinical study team for further consultation with the pharmacy manual owner.

